
1.2.5 Excision repair cross-complementation group 1 (ERCC1)

ERCC1 forms a heterodimer with XPF and as a unit, they perform the 5' incision which is specific to excision of Pt-DNA adducts.[49] Greater levels of total ERCC1 mRNA and full length ERCC1 mRNA were found in ovarian cancer tissues resistant to platinum-based chemotherapy.[42] The most widely studied polymorphism is 19007C>T (Asn118Asn), in which

the variant T allele was correlated to better response to platinum-based chemotherapy in epithelial ovarian cancer.[50] and oxaliplatin/5-FU combination chemotherapy in advanced colorectal cancer. [51] Another common SNP in ERCC1 is 8092C>A in 3' UTR. It was suggested that this variant may affect its mRNA stability which in turn results in reduced protein activity.[43] The variant A allele increased gastrointestinal toxicity in platinum treated NSCLC patients.[52] We have found that the ERCC1 N118N variant may occur at a lower frequency (around 20%) among African-Americans (unpublished data). It is unclear how this relates to the higher incidence of prostate cancer that is found in African-Americans. The frequency of the more widely studied polymorphism ERCC1N118N wild-type is also found to occur at around 20%, while variant alleles are about 80% (49% for the CT variant allele and 30% for the TT variant allele), in control groups of Caucasian men.. (unpublished data, please see Table on summary of key findings on variant DNA repair genes). Using these data, we propose that prostate cancer patients exhibiting ERCC1 variant alleles may have better response to a platinum agent such as satraplatin.

Table on summary of key findings on variant DNA repair genes in Caucasians and African-Americans (unpublished data)

Single Nucleotide Polymorphism	Genotype	Caucasian Counts (freq.)	African American Counts (freq.)	P VALUE
ERCC1N118N	CC	23(0.21)	96(0.76)	<0.001
	CT	53(0.49)	27(0.21)	
	TT	32(0.30)	4(0.03)	
	TOTAL	108	127	
ERCC1 C8092A	CC	77(0.53)	74(0.52)	N.S
	AC	59(0.40)	56(0.40)	
	AA	10(0.07)	11(0.08)	
	TOTAL	146	141	
ERCC2 K751Q	AA	49(0.42)	81(0.56)	<0.001
	AC	56(0.47)	57(0.40)	
	CC	13(0.11)	6(0.04)	
	TOTAL	118	144	
XRCC1 R399Q	GG			<0.001
	AG	49(0.46)	113(0.80)	
	AA	47(0.44)	26(0.19)	
	TOTAL	10(0.10)	2(0.01)	
		106	141	
XRCC1 R194W	CC	120(0.87)	133(0.90)	N.S
	CT	17(0.12)	14(0.09)	
	TT	1(0.01)	1(0.01)	
	TOTAL	138	148	

Single Nucleotide Polymorphism	Genotype	Caucasian	African American	P VALUE
		Counts (freq.)	Counts (freq.)	
PARP1 V762A	TT	80(0.67)	108(0.91)	<0.001 (ALLEL FREQ.)
	CT	32(0.27)	11(0.09)	
	CC	7(0.06)	0(0)	
	TOTAL	119	119	

1.2.6 Other DNA repair gene polymorphisms

Xeroderma pigmentosum group D: XPD gene, also known as ERCC2, encodes for a DNA helicase which catalyzes another rate-limiting step in NER pathway. A sibling-based study on prostate cancer correlated the variant homozygotes of Asp312Asn to slightly higher risk of prostate cancer and the variant allele of XRCC1 Arg399Gln adds great value to this effect [53]. And a most recent study showed that combined genotypes with at least one variant allele in XPD Lys751Gln and XRCC1 Arg399Gln were strongly related to improved survival in bladder cancer patients treated with platinum-based chemoradiotherapy [54]. However, some discrepant results were found in XPD polymorphisms with relationship to platinum chemotherapy. Possessing the wild-type allele of Lys751Gln increased the risk of suboptimal DNA repair though the Asp312Asn polymorphism were not found to affect DNA repair activity [55]. The wild-type allele Lys751Gln was associated with better response and longer survival in colorectal cancer patients received 5-fluorouracil/oxaliplatin chemotherapy, and this allele was in a strong linkage with Asp312Asn [56]. In addition, the variant allele of Asp312Asn was related to decreased overall survival, especially when combined with variant allele of XRCC1 Arg399Gln, in NSCLC patients treated with cisplatin/carboplatin [41].

Besides the NER pathways, other DNA repair proteins involved in base excision repair (BER) pathway, such as XRCC1 and PARP1 were also considered important because of their potential activities in removing platinum-DNA adducts.

X-Ray cross complementation group 1: XRCC1 is a principle player in BER pathway. It stimulates endonuclease activities following the excision of a damaged base and acts as both a scaffold and a regulator for other BER proteins [57]. The Arg399Gln change residues were firstly identified by Shen et al. This polymorphism resides in the C-terminal side of PARP-interacting domain [43]. The wild-type allele of Arg399Gln appeared more frequently in good responders to platinum-based chemotherapy in bulky cervical cancer patients [58]. Advanced colorectal cancer patients carrying variant allele of this substitution were more resistant to oxaliplatin/5-FU chemotherapy [59]. In addition, high expression levels of XRCC1 were found in bladder cancer patients with improved survivals following radical radiotherapy [60]. Published data have also shown correlations between the variant allele of Arg194Trp and increased risk of lung cancer [61], oral squamous cell carcinoma [62], and better response to platinum-based chemotherapy in advanced NSCLC [63].

Poly (ADP-ribose) polymerase-1: PARP1 is another member of BER complex and serves in detecting DNA interruptions. In response to these breaks, it recruits XRCC1 and other partners for further processing of the damages [64]. Overexpression of XRCC1 dramatically decreased PARP1 activity in vivo [64]. The variant allele of Val762Ala contributed to significantly lower PARP1 activity and increased prostate cancer risk [65]. Furthermore, PARP1 inhibitor was

proved to be able to increase the sensitivity of platinum compounds against platinum resistant ovarian tumor cells [66].

2 ELIGIBILITY ASSESSMENT AND ENROLLMENT

2.1 Eligibility Criteria

2.1.1 Inclusion Criteria

2.1.1.1 Patients must have histopathological confirmation of prostate cancer by the Laboratory of Pathology of the NCI or Pathology Department of the National Naval Medical Center or Walter Reed Army Medical Center prior to entering this study. Patients whose pathology specimens are not available may be enrolled in the trial if the patient has a clinical course consistent with prostate cancer and available documentation from an outside pathology laboratory of the diagnosis. In cases where original tissue blocks or archival biopsy material is available, all efforts should be made to have the material forwarded to the research team for use in correlative studies.

2.1.1.2 Patients must have metastatic progressive androgen-independent prostate cancer. There must be radiographic evidence of disease (by CT scan or bone scan) after primary treatment that has continued to progress despite hormonal agents. Progression requires that a measurable lesion is expanding, new lesions have appeared, and/or that PSA is continuing to rise on successive measurements. Patients must have progressive disease after receiving 1 prior docetaxel-based cytotoxic chemotherapy. Patients on flutamide for the prior 6 months must have disease progression at least 4 weeks after withdrawal. Patients on bicalutamide or nilutamide must have progression at least 6 weeks after withdrawal.

2.1.1.3 Patients may only have received 1 prior cytotoxic chemotherapy. For the purpose of this study, multiple courses of a taxane-based regimen may count as a single regimen. Multiple courses of a non-taxane agent or a combination chemotherapy regimen, administered in a similar fashion may count as a single regimen.

2.1.1.4 Patients must have a life expectancy of more than 3 months.

2.1.1.5 Patients must have a performance status of 0 to 2 according to the ECOG criteria.

2.1.1.6 Patients must have adequate organ function as defined below:

Leukocytes	$\geq 3,000/\mu\text{l}$
Absolute Neutrophil Count	$\geq 1,500/\mu\text{l}$
Platelets	$\geq 100,000/\mu\text{l}$
Total bilirubin	$\leq 1.5 \times$ institutional upper limits of normal*
AST(SGOT) and ALT(SGPT)	$\leq 2.5 \times$ institutional upper limit of normal
creatinine	$\leq 1.5 \times$ institutional upper limits of normal
OR	
Creatinine clearance	$\geq 60 \text{ mL/min}/1.73 \text{ m}^2$ for patients with creatinine levels above institutional normal.

*Except patients with Gilbert's disease who may proceed despite elevated total bilirubin

2.1.1.7 Patients must have recovered from any acute toxicity related to prior therapy, including surgery. Toxicity should be \leq grade 1 or returned to baseline.

- 2.1.1.8 Hormonal profile: all patients who have not undergone bilateral surgical castration must continue suppression of testosterone production by appropriate usage of GnRH agonists.
- 2.1.1.9 Patients must not have any ongoing malignancies requiring active therapy.
- 2.1.1.10 Patients must be able to understand and sign an informed consent form.
- 2.1.1.11 Concurrent use of bisphosphonates will be allowed if patients have previously been on it; if patients are not on bisphosphonates at the time of study enrollment, bisphosphonates may be started at cycle 2.
- 2.1.1.12 Patients who require hematopoietic growth factor support (e.g. epogen, darbepoetin), but not myeloid growth factors (except after cycle 1 day 1 if clinically indicated), NSAIDs, and other maintenance medications prior to study entry will be allowed to continue their supportive therapies.
- 2.1.1.13 Results from embryo-fetal development indicated that satraplatin should be considered a teratogen in women of childbearing potential and hazardous in respect to spermatogenesis for men. For this reason, men must agree to use adequate contraception (abstinence; hormonal or barrier method of birth control) prior to study entry and for the duration of study participation.
- 2.1.1.14 Patients must be able to swallow capsules
- 2.1.1.15** Patients on chronic stable steroids (equivalent to no more than 10 mg of prednisone daily dose) used for non-cancer treatment may be allowed on study

2.1.2 Exclusion Criteria

- 2.1.2.1 Patients who have had prior treatment with satraplatin or other platinum containing compounds will be excluded.
- 2.1.2.2 Patients may not be receiving any other investigational agents.
- 2.1.2.3 Patients with known active brain metastases are excluded from this clinical trial because of their poor prognosis and because they often develop progressive neurologic dysfunction that would confound the evaluation of neurologic and other adverse events.
- 2.1.2.4 History of allergic reactions attributed to compounds of similar chemical or biologic composition to satraplatin or prednisone.
- 2.1.2.5 Uncontrolled intercurrent illness including, but not limited to ongoing or active serious infection, symptomatic congestive heart failure, unstable angina pectoris, or psychiatric illness/social situations that would limit patient compliance with study requirements.
- 2.1.2.6 Prior radiation therapy to > 30% of the bone marrow, or who have received strontium-89, rehenium-186, or rhenium-188 will be excluded from this trial. Patients who have received prior radiotherapy must have recovered from acute toxicity due to radiation. Patients who have received samarium-153 are eligible for the study because samarium has a significantly reduced half-life compared to aforementioned isotopes.

2.1.2.7 Patients with immune deficiency are at increased risk of lethal infections when treated with marrow-suppressive therapy. Therefore, HIV-positive patients are excluded from the study.

2.1.2.8 Patients with a history of major gastrointestinal surgery or pathology likely to influence absorption of oral medications, like bypass surgeries, Whipple's procedure, or any surgery that would impair reliable absorption of oral drugs.

2.1.2.9 Patients with a disease where corticosteroids are contraindicated, e.g. active gastric or duodenal ulcer, or poorly controlled insulin dependent diabetes. Patients with well-controlled insulin-dependent diabetes mellitus may be considered, providing they understand their glucose levels will increase, and their insulin dose will require adjusting.

2.1.2.10 Because no dosing or adverse event data are currently available on the use of satraplatin in patients <18 years of age, children are excluded from this study.

2.2 Research Eligibility Evaluation

2.2.1 Imaging Studies (Baseline- obtained within 4 weeks prior to enrollment):

- Technetium-99 Bone Scintigraphy,
- Chest X-ray,
- CT scan of chest, abdomen and pelvis

2.2.2 Laboratory Evaluation (Baseline- obtained within 16 days prior to enrollment)

- Hematological Profile: CBC with differential and platelet count, PT, aPTT, fibrinogen.
- Biochemical Profile: electrolytes, BUN, creatinine, AST, ALT, alkaline phosphatase, total bilirubin, calcium, phosphorus, albumin, magnesium, uric acid, total protein, glucose, albumin, amylase, lipase, testosterone level.
- PSA (baseline within 7 days prior to enrollment)
- Electrocardiogram (performed within 21 days prior to enrollment); Patients with a history of myocardial infarction or cardiac arrhythmias will undergo evaluation by cardiology.

2.3 Patient Registration

Authorized staff must register an eligible candidate with NCI Central Registration Office (CRO) within 24 hours of signing consent. A registration Eligibility Checklist from the web site (<http://intranet.cancer.gov/CCR/welcome.htm>) must be completed and faxed to [contact].

After confirmation of eligibility at Central Registration Office, CRO staff will call pharmacy to advise them of the acceptance of the patient on the protocol prior to the release of any investigational agents. Verification of Registration will be forwarded electronically via e-mail. Please note, it is very important for all registrars to acquire encrypted e-mail from NIH Help Desk, since the verification of registration includes patient's information. A recorder is available during non-working hours.

3 Study Design

This trial will be conducted using a single stage design. However, to protect against the unlikely possibility that the agent will be associated with overall progression free survival which is substantially below what is expected based on results from other trials, an early stopping rule will be implemented as follows. After 20 patients have been enrolled and 6 months have passed since the 20th patient has enrolled, the proportion of patients who have attained 6 months without progression will be determined. If this fraction is no greater than 3/20 (15% who have attained 6 month progression free survival), then the trial will cease enrolling further patients because a one-sided 90% upper confidence bound on 3/20 is 30.4%, which would only indicate at best a modest probability of marginal consistency with what would be expected as the overall outcome using satraplatin. Similarly, genotyping for ERCC1 will also be performed after the 20th patient to test whether we are achieving the true probability of ERCC1 wild type proportion of 20% as indicated in earlier studies (in Caucasians). If the true probability is as shown, the probability of having 0 or 1 with WT genotype is tabled:

True WT proportion	Probability of getting 0 or 1 with WT
0.2	7%
0.1	39%
0.05	74%

Thus, if only 0 or 1 patient out of the first 20 patients should have ERCC1 WT genotype, then this would be more consistent with a 0.05 rather than a 0.20 true rate of WT. If this turns out to be the case, then we would re-evaluate the procedure for enrolling subjects to try to increase the proportion of patients with ERCC1 WT and amend the protocol accordingly. Otherwise, accrual to the full 66 patients will continue. See section 9.. Statistical analysis for further review of statistical design.

3.1 Drug Administration

3.1.1 Satraplatin administration

Satraplatin will be administered in an outpatient basis. This is to allow for pharmacokinetic samples to be obtained as outlined in section 3.4.1.1. Reported adverse events and potential risks are described in Section 6. Appropriate dose modifications for satraplatin are described in Section 3.3. No investigational or commercial agents or therapies other than those described below may be administered with the intent to treat the patient's malignancy.

Satraplatin is supplied as 1 x 5 capsules in blister strips. There are two strengths of capsules, one with 10 mg dose and the other with 50 mg dose. Patient's dose will be calculated based on body surface area as 80 mg/m^2 dose to be given daily x 5 days, every 35-days cycle. The total dose of satraplatin delivered should be rounded to the nearest 10 mg dose, (i.e., if total dose is < 165 mg, deliver 160 mg; if total dose > or = 165 mg, deliver 170 mg) after calculation of patient BSA. Patients are to swallow the capsules whole with approximately 125 ml - 250 ml of any clear liquids. Capsules should be taken on an empty stomach (no food for 2 hours before or 1 hour after dosing). Satraplatin will be given as self-administered oral doses of 80 mg/m^2 for days 1-5 every 35 days. Patients will be asked to maintain a diary to document consumption of satraplatin

as outlined in section 8 and Appendix B.

Patients will be required to have weekly blood counts drawn for the first 3 cycles of the study at an outside laboratory or at the Clinical Center given the risk of decreased white cell count and platelet count from satraplatin.

3.1.2 Prednisone administration

Prednisone 5 mg will be administered two hours prior to satraplatin (along with antiemetic, outlined in section 4.2) in AM and another 5 mg of prednisone in PM, on days 1-5. On days 6-35, patients will continue Prednisone 5 mg twice daily. Therefore, prednisone is given continuously twice daily throughout the 35-day cycle.

3.2 Treatment Modifications

Toxicities will be described using the Common Terminology Criteria for Adverse Events version 3.0 (CTCAE v3). The following adjustment will only apply if the toxicities reported are attributed by the investigator to be related to satraplatin and prednisone therapy.

3.2.1 Dose modification for satraplatin:

Dose reductions will be according to the following rules for satraplatin:

For Grade 1 toxicity, no treatment interruption or dose reduction for either satraplatin or prednisone, will be made. For Grade 2 or greater toxicity, subsequent treatment with satraplatin will be followed as shown in the table below and following the dose reduction schema.

Non-Hematologic toxicity Dose adjustments and reductions		
Grade of Non-hematologic toxicity (CTCAE v3.0)	Management/dose adjustment	Dose reduction
Grade 1	None	None
Grade 2 nausea, vomiting or diarrhea	Maintain dosing with symptomatic treatment; Repeat dosing if all tablets appear in emesis	None
Persistent Grade 2 nausea, vomiting or diarrhea despite symptomatic treatment that remains unacceptable (intolerable) to the patient	Decrease from 80mg/m ² to 60 mg/m ² **	Decrease by 20 mg/m ²

Non-Hematologic toxicity Dose adjustments and reductions		
Grade of Non-hematologic toxicity (CTCAE v3.0)	Management/dose adjustment	Dose reduction
Grade 3 clinical, Grade 3 or 4 laboratory abnormalities which are associated with clinical signs and symptoms that are felt to be drug-related	Hold satraplatin and reevaluate the patient at least weekly until toxicity improves to \leq Grade 1 or pre-treatment baseline*	Decrease by 20 mg/m ² (i.e., if patient is at 80mg/m ² /day dose, decrease to 60mg/m ² /day)**
Grade 4 clinical (except pulmonary embolism without significant hypoxia and hemodynamic instability)	Off-study	
Grade 4 vomiting or diarrhea that can not be controlled by medical treatment and that occurs after one dose reduction	Off-study	

*Treatment delay should not be >8 weeks from Day 1 of prior cycle or >3 weeks from the start of next scheduled cycle; otherwise, patient will be taken off-treatment.

**If patient is already at 60mg/m², decrease further to 40mg/m²; No further dose reduction after 40mg/m² will be permitted

-Non-hematologic toxicity ascribed to study drugs must resolve to baseline or \leq grade 1, with the exception of alopecia; or \leq grade 2 for pain in order for re-treatment to continue.

3.2.2 Hematologic Toxicity:

Given that hematologic toxicity is one of the major toxicities that may be experienced, all patients should have complete blood count measured and recorded weekly during the first 3 cycles and as needed, thereafter. However, if the ANC is $\leq 0.5 \times 10^9/L$ or platelets are $\leq 25.0 \times 10^9/L$, CBC with differential must be redrawn more frequently, at least two times per week, until resolved.

Dose changes for satraplatin will be made based only on changes in the neutrophil and platelet counts. Satraplatin will be discontinued if neutropenia ($\leq 0.5 \times 10^9/L$) lasting ≥ 5 days or thrombocytopenia ($\leq 25 \times 10^9/L$) lasting ≥ 5 days despite dose reduction to 40mg/m²/d occurs, or if there is retreatment delay of > 8 weeks from Day 1 of prior cycle, due to study drug-related hematologic toxicities.

No growth factor support will be given prophylactically prior to starting satraplatin.

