7.1 Criteria for Removal from Protocol Therapy

- Clinical progression of disease, appearance of one or more new lesions and/or unequivocal progression of existing lesions.
- Clear radiographic progression of disease by RECIST Criteria version 1.0
- Grade 3 or greater toxicity attributed to treatment, as defined in section 3.3 that does not resolve to grade 1, or pre-treatment baseline, within 3 weeks from next scheduled cycle.
- Neutropenia ($\leq 0.5 \times 10^9/L$) or thrombocytopenia ($\leq 25 \times 10^9/L$) that occurs despite dose reduction to 40mg/m²/d, or if there is retreatment delay of > 8 weeks from Day 1 of previous cycle
- Grade 4 vomiting or diarrhea that cannot be controlled by medical treatment and that occurs after one dose reduction will warrant discontinuation of satraplatin.
- Intolerable or limiting toxicity while on dose reduction of 40 mg/m².
- Intercurrent illness or medical circumstances. If at any time the constraints of this protocol are detrimental to the patient's health, the patient may be removed from protocol therapy and reasons for withdrawal will be documented.
- Patient requests to be taken off treatment. Reasons for withdrawal will be documented.
- Noncompliance with protocol guidelines (patient removed at discretion of Principal Investigator).
- General or specific changes in the patient's condition render the patient unacceptable for further treatment in the judgment of the investigator.
- Subject death.
- Patients who meet criteria for PSA progression may continue on treatment unless they meet the above criteria.

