7.2 Post Treatment Evaluation

Once the patient is no longer receiving treatment (as per section 3.9), he may receive follow-up calls to monitor his well-being and progress. For patients who are taken off treatment due to treatment toxicities, a follow up evaluation will be conducted within a month and if subject will be taken off study. The phone calls will likely be annual though no specific guidelines shall be set.

7.3 Off Study Criteria:

The patient will be considered off study upon either patient's death or patient's decision to no longer participate in the study or post treatment follow-up.

7.3.1 Off-Study Procedure:

Authorized staff must notify Central Registration Office (CRO) when a patient is taken off-study. An off-study form from the web site (<http://intranet.cancer.gov/CCR/welcome.htm>) main page must be completed and faxed to [contact].

8 Data Collection

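### The protocol's rules for attributed grade 4 clinical toxicity do not agree (Section 3.2.1 internally, and with 7.1), and its use of off-study contradicts 7.3, leaving 6-month progression follow-up unclear

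*Protocol*

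**What the plan says.** **Section 3.2** applies to attributed toxicity only: "The following adjustment will only apply if the toxicities reported are attributed by the investigator to be related to satraplatin and prednisone therapy". The non-hematologic table in **3.2.1** then has these rows:

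- Grade 3 clinical toxicity, and symptomatic grade 3 or 4 laboratory abnormalities: hold satraplatin until recovery, then reduce the dose. A footnote limits the delay to 8 weeks from Day 1 of the prior cycle, or 3 weeks past the next scheduled start, after which the patient is off-treatment.
- A general row, "Grade 4 clinical (except pulmonary embolism without significant hypoxia and hemodynamic instability", for which the only action given is to take the patient off-study.
- A narrower row, "Grade 4 vomiting or diarrhea that can not be controlled by medical treatment and that occurs after one dose reduction", with the same action.

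**Section 7.1** lists criteria for removal from protocol therapy. Two concern this kind of event:

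- The first is a bullet on "Grade 3 or greater toxicity attributed to treatment, as defined in section 3.3". Its condition for removal is lack of recovery, that is, toxicity "that does not resolve to grade 1, or pre-treatment baseline, within 3 weeks from next scheduled cycle".
- The second repeats the narrower row of the table: "Grade 4 vomiting or diarrhea that cannot be controlled by medical treatment and that occurs after one dose reduction will warrant discontinuation of satraplatin".

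**Section 7.3** defines off-study: "The patient will be considered off study upon either" death or the patient's own decision to stop participating. Toxicity is not among the reasons.

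**Section 7.2** gives patients who leave treatment for toxicity one evaluation within a month, followed by an unfinished clause about being taken off study. Later contact is by telephone, probably yearly, with no fixed schedule.

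**The concern.** The most severe non-fatal toxicity should lead to the same action whichever section the investigator opens. Here the sections give different answers, and two rows of one table overlap with different conditions.

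The statistical stake is endpoint ascertainment. The primary analysis in Section 9 compares the proportions of patients without progression at 6 months by ERCC1 genotype. A patient labelled off-study for toxicity may be read as having left follow-up. A patient who has only stopped protocol therapy may still be scanned. The protocol does not say which applies, so 6-month status could be missing for some patients because of an ambiguous label.

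**Working it through.** No figure in the plan is at issue, so the check sets the rules side by side for the same patient: attributed, non-hematologic, grade 4 clinical toxicity, not yet at the lowest dose level (7.1 has a separate criterion for intolerable toxicity there).

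| Case | 3.2.1 table | 7.1 |
|---|---|---|
| (a) Not vomiting or diarrhea, not the excepted embolism; resolves within the window | Off-study | No toxicity criterion met |
| (b) Same, does not resolve | Off-study | Removed, once the window has passed |
| (c) Vomiting or diarrhea, controlled or before any dose reduction | General row: off-study. Specific row: condition not met | Specific bullet: condition not met |
| (d) Excepted pulmonary embolism | Exempt from the off-study row; no action stated | Falls in the bullet for grade 3 or greater |

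**Step 1, inside the table.** The general row takes in every grade 4 clinical toxicity but one defined type of embolism. Vomiting and diarrhea are not excepted. Any patient meeting the specific row has therefore already met the general one, and the specific row's two conditions can have effect only if those events are exempt. The table does not say that they are.

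**Step 2, table against 7.1.** Both apply to attributed toxicity, so scope does not separate them. The 7.1 bullet starts at grade 3 and has no upper limit, so its wording includes grade 4, and its trigger is non-resolution. No other 7.1 toxicity criterion reproduces the general grade 4 row. The outcomes diverge in case (a); in case (b) both end treatment and differ at most in timing.

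**Step 3, the cross-reference.** The 7.1 bullet cites Section 3.3, but Section 3 now ends at 3.2. Section 3.1.1 also sends the reader to 3.3 for satraplatin dose modifications, so 3.3 is evidently the former number of the present 3.2.

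**Step 4, the term.** One event shows the mixed usage. A cycle is 35 days, or 5 weeks, and 5 + 3 = 8 weeks, so the two delay limits coincide. For a delay beyond 8 weeks, the 3.2.3 table says off-study, while the 3.2.1 footnote and the text of 3.2.4 say off-treatment. Under 7.3 neither delay nor toxicity is a ground for off-study.

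**Step 5, the endpoint.** Restaging is every 2 cycles: 2 × 35 = 70 days, or 10 weeks. Section 9 ties the scans to every 10 weeks of treatment until progression. A patient removed before the first restaging has no scheduled post-baseline scan, and 7.2 supplies none. The protocol does not state how his 6-month status is obtained.

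**The case against.** The strongest reply concerns Step 2. Section 7.1 lists grounds that suffice for removal and never says they are the only ones; failing to meet one bullet does not order continued treatment. If 3.3 means the present 3.2, the bullet points back to the table. The words for grade 3 or greater could then refer to the hold row, which includes grade 4 laboratory abnormalities and whose footnote has the same 3-week limit. The retreatment sentence in 3.2.4 is also printed beneath the 3.2.1 table, so it may concern only patients whom the table has not already removed.

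This has force. A reader might infer that one section removes the patient at once and the other requires that he be kept on treatment. The documents do not support that: the table sets no timing, and 7.1 does not mandate continuation. What stands is that the 7.1 bullet is not limited to laboratory events and that no 7.1 criterion matches the grade 4 row.

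On vomiting and diarrhea, one can read the specific row as overriding the general one. That is sensible drafting practice, but the table states its exceptions and omits these. It would also leave other grade 4 toxicity unresolved.

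On off-study, the loose usage suggests that off-treatment may be all that was meant. That is likely, but it confirms the need to correct the term. It is also true that reconciling the grade 4 rows alone would not settle 6-month follow-up; 7.2 and Section 9 need their own sentence.

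**Conclusion.** The inconsistency is real. Two parts rest on the text alone: the overlapping rows in the 3.2.1 table, and off-study used for toxicity against its definition in 7.3. The mismatch between 3.2.1 and 7.1 is softer. It is a missing matching criterion plus a dead cross-reference, with different outcomes for a grade 4 clinical toxicity that resolves within the window.

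The size cannot be given. The protocol reports no grade 4 clinical rate for this regimen. Section 1.2.2 names diarrhea among the dose-limiting toxicities in phase I, but also describes nausea, vomiting and diarrhea as generally mild to moderate. Hematologic events have their own rules and fall outside the grade 4 conflict, though the 3.2.3 table shares the off-study wording problem.

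A reader might go further and infer a calculable loss of power, or removals concentrated in variant carriers that bias the genotype comparison. The documents support neither. They give no removal rate and do not say that a patient removed for toxicity counts as progressed. They offer no evidence that toxicity on satraplatin in this population differs by genotype; Section 9 plans only a possible tabulation. The point should be made without such figures.

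This should be corrected because it governs who stays on treatment and leaves ascertainment of the primary endpoint uncertain.

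**What to change.** 1. Reconcile the 3.2.1 rows, 3.2.4 and 7.1 so that one rule covers attributed grade 4 clinical toxicity, including vomiting, diarrhea and the excepted embolism. Which rule applies is for the investigators to set.
2. Correct the references to Section 3.3 in 7.1 and 3.1.1.
3. In the 3.2.1 and 3.2.3 tables, replace off-study with the 7.1 term, removal from protocol therapy, if that is what is meant. Use the same term in the 3.2.1 footnote and 3.2.4, and keep off-study for the 7.3 reasons.
4. Complete the unfinished clause in 7.2, and state there and in Section 9 that patients removed for toxicity continue to be assessed for progression to 6 months.

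Items 1 to 3 cost amendment wording only. Item 4 is also a wording change; it may add restaging visits for patients removed early, but no new type of assessment.
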